Legacy of the Special Olympics World Games Berlin 2023

NCT Number: NCT05871450

03.07.2025

Study design and participants

This quasi-experimental trial was performed in urban and municipal areas throughout Germany. Adults of any gender, race/ethnicity were eligible for participation if they resided in one of the a priori selected communities, were at least 18 years of age and part of one of the three stakeholder groups. The recruitment period, including the baseline measurement, commenced on March 14th 2023 and concluded on June 8th, 2023. The intervention (Host Town Program) was conducted from June 12th to 15th, 2023. The post intervention measurement took place from June 26th to July 15th, 2023 and the 6-months follow up measurement from November 29th, 2023 to December 31st, 2023.

The intervention group comprised residents from Host Towns, while the control group consisted of residents from municipalities that had not applied to become Host Towns (prior to the initiation of the study, 216 municipalities were selected by Special Olympics to deliver the Host Town Program). Host Towns and Control towns were constituted through a random selection process, stratified by municipality size. Of note, random selection was only feasible within the group of the Control Towns, while allocation to the intervention was not at random (Host Towns were defined by Special Olympics; nonequivalent groups design). The selection of municipalities was conducted from a range of urban and rural communities, encompassing large cities, medium-sized towns, small towns, and rural communities, in accordance with the categorisation of city and community types as delineated by the Federal Institute for Research on Building, Urban Affairs and Spatial Development (Bundesinstitut für Bau-, Stadt- und Raumforschung., 2017).

Intervention

The Host Town Program facilitated interaction and contact between people with and without intellectual disabilities to promote positive attitudes towards people with intellectual disabilities in Host Towns in Germany. Therefore, in every Host Town a Host Town Program leader organized inclusive activities. These activities included sport festivals, school visits, workshops, and festivals. Furthermore, Host Towns functioned as hosts for the international delegations of Special Olympics athletes. The activities were planned in cooperation with local stakeholders from sports clubs, schools, and political institutions. A preliminary study was conducted in which 56 leaders of the Host Town Program were invited to provide feedback on the planned content of the program. As a result, 89% of Host Town Program leaders planned to collaborate with regional sports clubs, 50% stated that they involve schools, 39% intended to engage organizations for people with intellectual disabilities, and 4% wanted to involve kindergartens.

To prepare for the Host Town Program, monthly trainings for Host Town Program leaders have been conducted by the Berlin 2023 LOC. The objective of the training program was to provide program leaders and stakeholders with the knowledge and skills necessary to plan and implement inclusive events in collaboration with people living with intellectual disabilities.

Therefore, the following teaching and learning materials were made available for use:

Guidelines for the promotion of inclusion in sporting activities, activity cards and project outlines for the promotion of inclusion in sports, guidelines for the establishment of inclusive communities and workshops for people with intellectual disabilities on the promotion of healthy and physically active lifestyles. After the Host Town Program, in August 2023, a series of sustainability workshops were conducted for the Host Town Program leaders and other community members involved in the local programs. The objective of these workshops was to facilitate the dissemination of knowledge, best practice advice, and feedback among

participating communities. Additionally, these workshops aimed to establish sustainable interventions and networks.

Primary outcomes

The primary outcomes of the present study was to ascertain participants' attitude change toward people with intellectual disabilities, measured by the self-administered Attitudes Toward Intellectual Disability – Short Form (ATTID-SF) questionnaire (D. Morin, Crocker, et al., 2013; D. Morin et al., 2019) translated into German. Attitude change was measured at post intervention and 6-months follow up.

The ATTID-SF assesses three components of attitudes according to a multidimensional model (Findler et al., 2007). Firstly, what positive and negative feelings do I have toward people with intellectual disabilities (emotion). Secondly, what do I think and know about people with intellectual disabilities and what perceptions, beliefs and opinions do I have (cognition). Thirdly, how do I behave toward people with intellectual disabilities (behavior). In collaboration with the author of the original questionnaire and considering the guidelines for intercultural adaptation, the questionnaire was translated into German and validated in a pilot study. The short form of the ATTID questionnaire consists of 35 questions (items) on a 5-point Likert scale (ranging from [1] strongly agree to [5] strongly disagree). High scores indicate negative attitudes toward people with intellectual disabilities. The questions are grouped into five factors: interaction, sensitivity or tenderness, discomfort, knowledge about the abilities of people with intellectual disabilities, and knowledge about the causes of intellectual disabilities. For each category, a mean is calculated. However, due to the factor structure, it is not recommended to calculate an overall score (D. Morin et al., 2019). Furthermore, data on socio-demographic characteristics, including age, gender, and level of education, were collected at baseline.

Statistical analysis

The minimum sample size was determined using an priori power analysis. The analysis was based on existing research that reported small effect sizes in attitudinal change trials (Diane Morin et al., 2023; Varughese & Luty, 2010; Walker & Scior, 2013). The only trial on attitudinal change study in the context of Special Olympics was conducted by Diane Morin et al. (2023) with small Cohen's d effect sizes for the sensitivity or tenderness factor ($d = 0.32$) and interaction factor ($d = 0.25$). We anticipated a mean effect size of $d = 0.29$, calculated from these two factors, for our sample size calculation. We assumed a two-sided t -test, an alpha level of 0.05, and a statistical power of 80%. Using G*Power 3.1.9.7 (Faul et al., 2009), we calculated a total sample size of 296 participants. In addition, we assumed an average dropout rate of 48% after baseline measurement, given the literature on dropout rates for attitude change in Special Olympics settings of 34% (Sullivan & Masters Glidden, 2014) and of 63% in average online surveys for randomly selected samples (Wu et al. (2022)). The aim was therefore to achieve a total sample size of 700 participants.

Descriptive statistics are presented using mean and standard deviation (SD) for continuous variables (unless otherwise stated). We used t -tests, Mann-Whitney U tests, or Chi-square tests to compare differences between groups (e.g., intervention vs control), depending on the distribution of metric data and the level of measurement. Associations of missingness at follow-up with baseline characteristics were assessed using binary logistic regression models.

A general linear model was used for analyses. All models were derived from complete cases according to allocation. K. Scior (2011) published a study identifying age and education as significant predictors of attitudes toward people with intellectual disabilities. Additionally, prior contact through sports has been demonstrated to be associated with less negative behavioral and affective attitudes (Albaum et al., 2022). Consequently, all models were adjusted for age, education, participation in sports, physical activity with people with intellectual

disabilities, and baseline outcomes. For sensitivity analysis, we further adjusted for gender, income, and work with people with intellectual disabilities. The literature for this three confounders is inconsistent (D. Morin, Rivard, et al., 2013; Scior, 2011; Slater et al., 2020). Furthermore, analysis were repeated after excluding outliers ($\pm 3SD$ away from the mean). The significance level was set at $p < 0.05$ (two-sided). The statistical analyses were performed using IBM SPSS Statistics (Version 30).

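### The 80% power rests on an averaged effect that no described endpoint has, and on a sample size that does not match the stated two-sided test; for the interaction factor the power is about 66% at the expected 364 completers

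*Combined protocol and SAP*

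**What the plan says.** The sample size paragraph of the Statistical analysis section takes its planning effects from one earlier Special Olympics trial, which reported "small Cohen's d effect sizes for the sensitivity or tenderness factor" (0.32) and for the interaction factor (0.25). The plan adopts d = 0.29, a mean "calculated from these two factors, for our sample size calculation". The test is then specified: "We assumed a two-sided t -test, an alpha level of 0.05, and a statistical power of 80" per cent. From this, "we calculated a total sample size of 296 participants". For attrition, "we assumed an average dropout rate of 48% after baseline measurement", and the recruitment target is 700.

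The Primary outcomes section describes five factors, with a mean for each, and says of a total that "it is not recommended to calculate an overall score". Neither section defines a score that combines interaction with sensitivity or tenderness. The analysis text sets two-sided 0.05 and adjusts every model for the baseline outcome, age, education and sport-related contact.

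**The concern.** A power statement is useful only if it belongs to a test that will be carried out. Here it belongs to the midpoint of two factors. If each factor is tested on its own, the factor with the smaller expected effect has less power than stated and the other has more. Discomfort and the two knowledge factors have no planning effect at all.

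A second fault lies in the same calculation: the stated inputs do not lead to 296. A correction of the averaging alone would leave that contradiction in place, and a correction of the sidedness alone would leave the interaction factor short.

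What is at stake is how a null result is read. A non-significant interaction result would be taken as coming from a test with an 80% chance of detecting the expected effect. On the plan's own effect size and expected completers, the chance is nearer two in three.

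**Working it through.** **Inputs from the plan.** d = 0.32 and 0.25, planning value 0.29; alpha 0.05, two-sided; power 80%; total 296; dropout 48%; recruitment target 700. **Assumption:** equal groups, because no allocation ratio is given.

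**Step 1: the averaged effect.** (0.32 + 0.25)/2 = 0.285, which the plan rounds to 0.29.

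**Step 2: reproduce 296.** The normal approximation per group is n = 2(z_alpha + z_beta)²/d², with z_beta = 0.8416.
- Two-sided, as stated: 2(1.9600 + 0.8416)²/0.29² = 186.7, so 187 per group and 374 in total. The exact noncentral t calculation gives 188 per group, 376 in total.
- One-sided: 2(1.6449 + 0.8416)²/0.29² = 147.03, so 148 per group and 296 in total. The noncentral t also gives 296, with power 80.1%.

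The stated two-sided inputs do not reproduce 296; a one-sided alpha of 0.05 reproduces it exactly. A paired two-sided test would need 96. Unequal groups move the two-sided total further away (423 at 2:1, 500 at 3:1).

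**Step 3: total needed for 80%, two-sided (noncentral t).**

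| d | Total N |
|---|---|
| 0.32 | 310 |
| 0.29 | 376 |
| 0.285 | 390 |
| 0.25 | 506 |

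So 296 falls short of two-sided 80% for every effect in the paragraph, including the larger one.

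**Step 4: two-sided power at fixed N.** The noncentrality is d·√(n/2), with n per group. For d = 0.25 and n = 148 it is 0.25 × √74 = 2.151. Expected completers are 700 × (1 − 0.48) = 364.

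| Total N | d = 0.25 | d = 0.29 | d = 0.32 |
|---|---|---|---|
| 296 | 57.3% | 70.1% | 78.3% |
| 364 | 66.2% | 78.8% | 86.1% |
| 376 | 67.6% | 80.1% | 87.2% |

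**Step 5: separate the two causes.**
- Sidedness, at 296 and d = 0.29: 80.1% − 70.1% = about 10 points.
- Averaging, two-sided, moving from d = 0.29 to 0.25: 70.1% − 57.3% = 12.8 points at 296; 78.8% − 66.2% = 12.6 at 364; 80.1% − 67.6% = 12.5 at 376.
- Averaging, if 296 is read as one-sided: 80.1% − 69.2% = 10.9 points.

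Averaging therefore costs the interaction factor 11 to 13 points, whichever way the sidedness is settled.

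**Step 6: sensitivity to baseline adjustment.** The documents give no correlation r between baseline and follow-up. As an assumption, take d in raw SD units and replace it with d/√(1 − r²). At d = 0.25:

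| r | N = 296 | N = 364 |
|---|---|---|
| 0.3 | 61% | 70% |
| 0.5 | 70% | 78% |
| 0.7 | 85% | 91% |

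**The case against.** **The recruitment target covers most of the shortfall.** Inflating 296 for 48% dropout needs only 296/0.52 = 569.2, so 570, yet the plan aims for 700. The 364 expected completers give 78.8% at d = 0.29, close to the stated 80%. This stands, and it is why 364 rather than 296 is the fair basis for a power statement. It does not rescue the interaction factor, which reaches 66%.

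**The models adjust for baseline.** This also stands as a possibility. With a baseline correlation of 0.7, interaction power would pass 80% even at 296. But the plan gives no correlation and takes no credit for adjustment, and it does not say which SD standardises the cited effects. Clustering by municipality or unequal groups would work in the other direction. The t-test figures are therefore not firm in either direction, but they are the figures for the test the plan itself assumed.

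**A single central effect for related subscales is a planning choice, openly disclosed.** That is fair, and rounding 0.285 to 0.29 is ordinary. The choice still leaves the stated 80% attached to no endpoint.

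**Stronger readings to avoid.** A reader might infer that averaging alone brings the power from 80% down to 57%. It does not: about 10 of those points come from sidedness. A reader might also call the interaction test a coin toss, but that uses the pre-dropout minimum, not the completers the plan expects. Nor do the documents show that a one-sided test was entered in the software; they show only that 296 agrees with one. Separate testing of each factor is a reasonable inference from the scoring and is not stated outright. No multiplicity procedure is described, so none is counted here.

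**Conclusion.** The point holds in two parts. The stated 80% is planned on an effect that no described endpoint has, and the stated total does not follow from the stated two-sided test. At d = 0.29, 296 gives about 70%, and 376 are needed for 80%. For the interaction factor, averaging removes a further 11 to 13 points, leaving about 66% at the 364 expected completers (57% at 296, 68% at 376). Sensitivity or tenderness is just short at 296 (78%) and adequately powered at 364 (86%), so the documents do not support calling the trial underpowered on every factor. For the remaining three factors the plan gives no basis for any power figure.

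These results assume an unadjusted two-sample t-test, two-sided alpha 0.05, equal groups, independent participants and the plan's own effect sizes and dropout.

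**What to change.** In the sample size paragraph:

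1. Reconcile the two-sided statement with 296. Either report 376 as the two-sided total for d = 0.29, or state that 296 came from a one-sided calculation and give its two-sided power of about 70%.
2. Remove the averaged effect size.
3. State two-sided power separately at the expected 364 completers: about 66% for interaction (d = 0.25) and 86% for sensitivity or tenderness (d = 0.32). Give the allocation ratio assumed, and say that the figures are for an unadjusted t-test.
4. Say that no power claim is made for discomfort or the two knowledge factors.

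The cost is a few sentences and a less favourable stated power. Recruitment closed in June 2023, so a larger sample for the smaller effect is no longer an option, and none is asked for. The change affects how null results are interpreted and requires no extra enrolment or data.

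### The stated minimum of 296 matches a one-sided calculation; for the two-sided t-test the plan describes, 296 gives about 70% power, not 80%

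*Combined protocol and SAP*

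**What the plan says.** All inputs are in the first paragraph of the Statistical analysis section of the combined protocol and SAP.

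- Test, level and power: "We assumed a two-sided t -test, an alpha level of 0.05, and a statistical power of 80" per cent.
- Effect: "We anticipated a mean effect size of" d = 0.29, the average of two factor-level effects (0.32 and 0.25) from an earlier Special Olympics study.
- Result, obtained in G*Power: "we calculated a total sample size of 296 participants".
- Attrition: "we assumed an average dropout rate of 48% after baseline measurement", followed by a recruitment target of 700.

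The last paragraph of the same section again specifies a two-sided test: "The significance level was set at" p < 0.05, two-sided. One-sided testing is mentioned nowhere. The sample-size text takes no credit for covariate adjustment, although the analysis models do adjust for baseline outcomes and other covariates.

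**The concern.** A two-sided comparison of two means at 5% and 80% power, with d just under 0.3, needs well over 300 participants, so 296 looked too small. It is the size one would expect from a one-tailed setting in the software.

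The minimum sample size and the 80% power are the planning figures that a report of this study will repeat. The analyses use complete cases, so readers will compare the number of completers with 296. If 296 belongs to a different test, a study reaching it would be called adequately powered when it is not, and a null result would be read as stronger evidence of no effect than it is.

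**Working it through.** **Inputs.** From the plan: d = 0.29, alpha = 0.05, target power 80%, two-sided, stated N = 296, dropout 48%, recruitment target 700. Assumed: two independent groups of equal size, because no allocation ratio is given.

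**Method.** Exact power of the two-sample t-test from the noncentral t distribution, with n per group, df = 2n − 2 and noncentrality d × √(n/2). The critical value is the 0.975 quantile of t for a two-sided test and the 0.95 quantile for a one-sided test.

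**Step 1: look for the plan's figure.** A quick check with the normal approximation, n per group = 2(z_alpha + z_power)²/d²:

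- Two-sided: 2 × (1.960 + 0.842)²/0.29² = 186.7, so 187 per group, 374 in total.
- One-sided: 2 × (1.645 + 0.842)²/0.29² = 147.03, so 148 per group, 296 in total.

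The exact calculation gives:

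| Test | Smallest n per group for 80% | Total N | Power at that N |
|---|---|---|---|
| Two-sided, 5% | 188 | 376 | 80.1% |
| One-sided, 5% | 148 | 296 | 80.1% |

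The one-sided test reproduces 296 exactly. The stated two-sided test does not.

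**Step 2: two-sided power at the stated N.** With n = 148, the noncentrality is 0.29 × √74 = 2.495, df = 294 and the critical value is 1.968. Power is 70.1%, so the chance of missing the planned effect is about 30%. The shortfall in N is 376/296 = 1.27, or 27%.

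**Step 3: could another reading give 296?**

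- Unrounded mean effect, d = 0.285: two-sided N = 390, and power at 296 is 68.6%.
- The larger cited effect, d = 0.32: two-sided N = 310.
- The smaller cited effect, d = 0.25: two-sided N = 506.
- Paired t-test, d = 0.29, two-sided: N = 96.
- Allocation 2:1, two-sided, d = 0.29: N = 423, and power at 296 is 65.0%.
- The effect for which 296 gives 80% two-sided power: d of about 0.327, above either cited factor.

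None of these returns 296.

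**Step 4: carry through to the recruitment target.**

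- Needed for 296 completers at 48% dropout: 296/0.52 = 569.2, so 570.
- Needed for 376 completers: 376/0.52 = 723.1, so 724.
- The target of 700 leaves 700 × 0.52 = 364 completers; two-sided power at d = 0.29 is 78.8%.
- At the 63% dropout that the plan also cites for online surveys, 700 × 0.37 = 259 completers; two-sided power is about 64%.

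**Step 5: what baseline adjustment could recover.** If the baseline correlates rho with the outcome, the required N shrinks by about 1 − rho². To bring 376 down to 296 needs rho² = 1 − 296/376 = 0.213, so rho is about 0.46. The plan states no correlation.

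**The case against.** Nobody can rescue the arithmetic, so the case for leaving the plan alone rests on consequence.

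**The target was 700, not 296.** At the plan's own dropout rate 364 people would remain and two-sided power would be 78.8%, about one point below the stated 80%. This stands. The error does not show that the trial was planned at 70% power overall, and it should not be reported that way. It does not clear the plan, though: 364 is below 376, 700 is below 724, and 296 is presented as the minimum. At the higher dropout rate the plan cites, the completers would fall below even 296.

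**The analysis adjusts for baseline.** With a correlation of about 0.46, 296 would give 80%; with 364 completers, a correlation of 0.30 would already give about 82%. This is a fair point about the power the analysis may really have. But the calculation is described as a plain t-test with no correlation, so adjustment cannot be the source of 296. Clustering of residents within towns, also left out of the calculation, would push power the other way; the documents give nothing from which to size it.

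**A one-tailed setting is inferred.** The documents do not say one was used. That is correct, so the wording should be that 296 matches the one-sided result. The mismatch between the stated test and the stated number is not an inference.

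**The study is finished.** Correcting the figure changes no estimate, test or p-value. True, and this bears on the form of the correction, since overwriting 296 would present 376 as if it had been planned. It is no reason to leave an incorrect power statement in a public plan.

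**Conclusion.** The concern holds. For the test the plan describes, 80% power at d = 0.29 requires 376 completers, not 296, and 296 gives 70.1%. The result assumes equal groups, the most favourable allocation; any imbalance widens the gap. It also takes the calculation as written, an unadjusted t-test on independent individuals.

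The error lies in the stated minimum and the power attached to it. At the recruitment target and assumed dropout the deficit is about one percentage point; it reaches about ten points if the study ended at its stated minimum.

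**What to change.** Correct the sample-size statement in the Statistical analysis section in one of two ways.

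1. Preferable now that follow-up is complete: keep 296 as the number that was calculated, and add that it corresponds to a one-sided test at 5%, that its two-sided power at d = 0.29 is about 70%, and that 376 completers are needed for 80%.
2. Replace 296 with 376, marked as a correction. The next step of the paragraph must then be reconciled too, because 376 completers at 48% dropout imply 724 recruits rather than 700.

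Either way, state the equal-allocation assumption and give the two-sided power at d = 0.29 for the number of completers actually reached, computed from the planned effect and not the observed one, alongside the confidence intervals. If credit for baseline adjustment is wanted, state the correlation it relies on.

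The cost is a sentence or two and a less favourable planning figure. Enrolment, models and significance level are untouched.

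### The recruitment target of 700 does not follow from 296 participants and 48% dropout (that gives 570), and against the stated two-sided test its apparent surplus disappears

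*Combined protocol and SAP*

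**What the plan says.** The sample size is justified in the first paragraph of the section Statistical analysis of the Combined protocol and SAP. It proceeds in four steps.

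- Effect size: "We anticipated a mean effect size of $d = 0.29$, calculated from these two factors, for our sample size calculation". The two factors have d = 0.32 and d = 0.25.
- Test: "We assumed a two-sided t -test, an alpha level of 0.05, and a statistical power of 80" per cent.
- Result: "we calculated a total sample size of 296 participants", using G*Power.
- Dropout and target: "In addition, we assumed an average dropout rate of 48% after baseline measurement", taken from two literature figures of 34% and 63%, and then "The aim was therefore to achieve a total sample size of 700 participants".

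No margin, rounding rule or other step stands between 296 and 700. The same section says that the models use complete cases, so the number of completers determines the power. It also says that every model adjusts for the baseline outcome and other covariates. The ratio of intervention to control participants is not stated.

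**The concern.** The wording presents 700 as the consequence of 296 and 48%, yet those inputs give a figure 130 lower. Someone who checks only that step would conclude that the trial recruited to a target well above its requirement. That impression depends on 296 being right for the stated test, and it is not. Two discrepancies act in opposite directions: 296 is too low for a two-sided test, and 700 is too high for 296 at 48% dropout. They nearly cancel, but the text discloses neither.

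This paragraph is the only power justification in the document. A reader weighing a null result needs to know what the target would have delivered under the plan's own assumptions, and cannot recover that from the text.

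**Working it through.** **Inputs** (all from Statistical analysis): d = 0.29; two-sided t-test; alpha 0.05; power 80%; calculated total 296; dropout 48%; target 700. Assumed, because not stated: two independent groups of equal size. Exact figures below use the noncentral t distribution; the normal approximation is shown so that they can be checked by hand.

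**1. Reproducing 296.** Per group, n ≈ 2(z_alpha + z_power)²/d².

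- One-sided 0.05: 2 × (1.645 + 0.842)²/0.29² = 147.0, so 148 per group and 296 in total. The exact calculation also gives 148 per group, with 80.07% power. This is the plan's figure.
- Two-sided 0.05: 2 × (1.960 + 0.842)²/0.29² = 186.7, so 187 per group and 374 in total. The exact calculation gives 188 per group, 376 in total.

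The printed 296 is therefore the one-sided result. With 296 completers the two-sided power is 70.1%.

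**2. Reproducing 700.** Recruited = completers/(1 − dropout).

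| Route | Result |
|---|---|
| 296/(1 − 0.48) | 569.2, so 570 |
| 296/(1 − 0.485), the unrounded mean of 34% and 63% | 574.8, so 575 |
| 296 × 1.48 (a common mistake) | 438.1, so 439 |
| 296/(1 − 0.34) | 448.5, so 449 |
| 296/(1 − 0.63) | 800 |
| 376/(1 − 0.48) | 723.1, so 724 |

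None gives 700. Working backwards, 1 − 296/700 = 57.7%, a dropout rate that is stated nowhere. The difference 700 − 570 = 130 is 23% of 570, too large for rounding.

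**3. What 700 delivers.** 700 × 0.52 = 364 completers, which is 376 − 364 = 12 (3.2%) below the two-sided requirement. Two-sided power at 364 is 78.8% for d = 0.29, and 77.4% for the unrounded mean d = (0.32 + 0.25)/2 = 0.285.

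**4. Range over the two cited dropout figures** (d = 0.29, two-sided, 1:1, unadjusted).

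| Dropout | Completers from 700 | Power |
|---|---|---|
| 34% | 700 × 0.66 = 462 | about 87% |
| 48% | 364 | 78.8% |
| 63% | 700 × 0.37 = 259 | about 64% |

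**5. Sensitivity to allocation.** Unequal groups raise the two-sided requirement from 376 to about 393 at 1.5:1 and about 423 at 2:1.

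**The case against.** The strongest reply is that no shortfall is shown for the analysis actually planned. The models adjust for the baseline outcome, and the sample-size calculation takes no credit for that. If d = 0.29 is on the unadjusted scale, which the documents do not say, adjustment divides d by √(1 − r²), where r is the correlation between baseline and outcome. An assumed r of 0.18 already brings 364 completers to 80.1% power, and an assumed r of 0.5 brings them to about 89%. This stands. A gap of about one percentage point against an unadjusted t-test cannot carry a claim that the trial was underpowered. Clustering by municipality and the several factor scores at two time points work the other way, and the documents give no figure for any of these effects.

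It can also be said that 700 exceeds what the plan's own 296 requires, that it is worded as an aim, and that the implied 57.7% dropout lies between the two cited rates. All true. But the text says that the target follows from 48%, and it mentions no rounding up or safety margin, so a deliberate margin would have to be supplied by the reader.

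A reader might also infer that 48% is lost at each of the two follow-up waves, which would leave 700 × 0.52 × 0.52 = 189 at six months. The documents do not support this: they assume one average rate after baseline and do not apply it twice.

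**Conclusion.** The derivation is wrong as written, in two places. The step from 296 and 48% to 700 fails on the document's own numbers, with no further assumption. The 296 does not match the stated two-sided test; that conclusion assumes equal groups, and unequal groups would widen the discrepancy.

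The practical size is modest. Because the two discrepancies largely offset each other, 700 comes within 12 completers of the two-sided requirement. What is lost is the apparent surplus of 130. The 78.8% figure rests on d = 0.29, 48% dropout, 1:1 groups and an unadjusted t-test, with no design effect, no multiplicity correction and no gain from baseline adjustment. The stronger conclusion, that the trial misses 80% power for its planned models, does not follow, because the documents do not give the quantities needed to settle it in either direction.

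**What to change.** Recruitment closed on June 8th, 2023, and the document is dated 03.07.2025, so a new calculation should not be presented as the a priori one. Keep 296 and 700 on record as the planned figures, and add a short correction to Statistical analysis stating that:

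- 296 corresponds to a one-sided alpha of 0.05, and the stated two-sided test needs 376 completers, or 724 recruited at 48% dropout;
- 700 does not follow from 296 and 48%, which give 570;
- 700 gives 364 expected completers and about 79% two-sided power, assuming 1:1 groups and an unadjusted t-test, before any design effect or multiplicity and without credit for baseline adjustment.

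Report the achieved number of completers per group at the post-intervention and six-month waves.

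The cost is a few lines of text. No extra enrolment or change to the analysis is needed; the only downside is a slightly less favourable stated power.

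### The programme is assigned and delivered by town but residents are analysed as independent, so any positive residual within-town correlation makes standard errors too small and the type I error exceed 5%

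*Combined protocol and SAP*

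**What the plan says.** **Design.** Under Study design and participants, municipalities are the units drawn: "Host Towns and Control towns were constituted through a random selection process, stratified by municipality size". The text then qualifies this. Random selection was feasible only among the control towns, and "allocation to the intervention was not at random (Host Towns were defined by Special Olympics; nonequivalent groups design". Arm follows from where a person lives: "The intervention group comprised residents from Host Towns".

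**Delivery.** Under Intervention, "in every Host Town a Host Town Program leader organized inclusive activities", planned with local partners. The planned mix varied: 89% of leaders surveyed beforehand meant to work with sports clubs, 50% with schools and 39% with disability organisations.

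**Analysis.** Under Statistical analysis, "A general linear model was used for analyses. All models were derived from complete cases according to allocation". The covariates are age, education, participation in sports, physical activity with people with intellectual disabilities, and the baseline outcome. All are measured on the individual. The sensitivity analyses do not address towns: "For sensitivity analysis, we further adjusted for gender, income, and work with people with intellectual disabilities", and outliers are excluded.

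**Sample size.** A two-sided t-test with d = 0.29, alpha 0.05 and 80% power is said to give 296 in total, raised to a target of 700 with 48% dropout in mind. No ICC or design effect is mentioned.

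**Not stated.** "216 municipalities were selected by Special Olympics to deliver the Host Town Program", but the document does not say how many host or control towns were sampled, or how many residents came from each.

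**The concern.** Everyone in a town has the same group label, programme leader, local activities and local context. The group contrast is therefore a comparison between towns, and variation between towns belongs in its standard error. A general linear model on residents leaves it out and counts each resident as a separate piece of evidence about the programme.

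The analysis covers five questionnaire factors at two follow-up times, all with the same model. To the extent that residents of a town remain alike after adjustment, confidence intervals are too narrow, p-values are too small, and a difference arising from a few unusual towns can be read as a programme effect. The sample size rests on the same independence assumption.

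**Working it through.** **1. The plan's own figure.** For a 1:1 two-sample t-test with d = 0.29, two-sided alpha 0.05 and 80% power, the total is 376 (374 by the normal approximation), not 296. The figure 296 (148 per arm) is reproduced by a one-sided test. At 296 completers, two-sided power is 70% before any clustering. This is a separate defect, noted here because the stated 80% cannot serve as the baseline for a clustering loss. The fairer baseline is the number expected from the target: 700 × (1 − 0.48) = 364 completers, where two-sided power is 79% if residents are independent.

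**2. Inputs.** From the documents: target 700, dropout 48%, d = 0.29, alpha 0.05 two-sided. Assumed: equal arms, equal town sizes, k = 20 to 120 towns over both arms, and ICC = 0.01 to 0.05. The ICC meant is the residual one, after baseline and covariate adjustment.

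**3. Formulas.**
- Completers per town: m = 364/k
- Design effect: DE = 1 + (m − 1) × ICC
- Actual type I error of the unadjusted test: 2 × [1 − Φ(1.96/√DE)]
- Effective N = 364/DE, with power from the noncentral t at that N, noncentrality d√N/2

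**4. One case in full.** For k = 20 and ICC = 0.05: m = 18.2; DE = 1 + 17.2 × 0.05 = 1.86; √DE = 1.364; 1.96/1.364 = 1.437; type I error = 15.1%. Effective N = 364/1.86 = 196, noncentrality 0.29 × √196/2 = 2.03, power 52%.

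**5. The range.**

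| Towns | m | ICC | DE | Type I error | Effective N | Power, unadjusted t-test |
|---|---|---|---|---|---|---|
| 120 | 3.03 | 0.01 | 1.02 | 5.2% | 357 | 78% |
| 120 | 3.03 | 0.02 | 1.04 | 5.5% | 350 | 77% |
| 120 | 3.03 | 0.05 | 1.10 | 6.2% | 330 | 75% |
| 60 | 6.07 | 0.01 | 1.05 | 5.6% | 346 | 77% |
| 60 | 6.07 | 0.02 | 1.10 | 6.2% | 331 | 75% |
| 60 | 6.07 | 0.05 | 1.25 | 8.0% | 290 | 69% |
| 20 | 18.2 | 0.01 | 1.17 | 7.0% | 311 | 72% |
| 20 | 18.2 | 0.02 | 1.34 | 9.1% | 271 | 66% |
| 20 | 18.2 | 0.05 | 1.86 | 15.1% | 196 | 52% |

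The power column uses degrees of freedom based on effective N. With degrees of freedom based on towns (20 − 2 = 18), the last row falls from 52% to 48%.

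**6. Check by simulation.** An ordinary t-test applied to data with random town effects (4,000 runs per scenario) rejected a true null in 10.4% of runs with 30 towns of 10 at ICC 0.05, and in 5.8% with 60 towns of 5 at ICC 0.01. The formula gives 10.4% and 5.5%.

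**7. Completers needed.** For 80% two-sided power with an unadjusted t-test, 376 × DE is about 384 at DE 1.02 and 700 at DE 1.86. Divided by 0.52, that is about 738 and 1,345 recruits, against a target of 700.

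**The case against.** **The size is unknown and may be small.** This stands. With 216 host towns in existence and selection spread over large cities, medium-sized towns, small towns and rural communities, many towns with few respondents each fit the text as well as 20 towns do. At 120 towns the type I error is only 5.2% to 6.2%. A reader might infer that the error rate is badly inflated for every primary result, or assume about 10 towns, where ICC 0.05 would give about 24%. The documents support neither: they give no town count and no ICC, and each factor and time point has its own residual correlation.

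**Baseline adjustment lowers the relevant ICC.** This stands in part. Stable differences in attitude between towns are partly absorbed by the baseline outcome. Town-specific effects that arise after baseline, from a particular leader or set of activities, are not.

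**The power loss is not established for the model actually used.** This also stands. The power figures above are for an unadjusted t-test. If d = 0.29 is on the raw-score scale and the baseline correlation were 0.6 (both assumptions), the standardised effect becomes 0.29/√(1 − 0.36) = 0.3625. Power at 20 towns and ICC 0.02 is then about 84% rather than 66%. The document gives no such correlation, so the offset cannot be calculated. A reader might infer that clustering is why the stated 80% is too high, but that figure belongs to N = 296 and already fails two-sided without clustering.

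**Allocation was not random anyway.** This is true, but confounding is a different problem and does not excuse a standard error that leaves out a source of variance.

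**Conclusion.** The omission is certain. Towns receive the programme, residents are analysed as independent, and nothing in the main models, sensitivity analyses or sample size allows for town. The direction follows for any positive residual within-town correlation when towns contribute more than one resident.

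The size is conditional. Under 364 completers, 20 to 120 towns and a residual ICC of 0.01 to 0.05, the design effect is about 1.02 to 1.86 and the type I error about 5.2% to 15%. That runs from negligible to enough to change conclusions, and a reader cannot tell which applies.

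On power, what can be said is that the calculation contains no design effect. Without baseline adjustment, power at 364 completers would go from 79% to between about 78% and 52%; the net position after adjustment cannot be computed from the document.

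**What to change.** - Replace the general linear model with a linear mixed model (SPSS MIXED, in the package already named) with a random intercept for municipality and Satterthwaite degrees of freedom. Cluster-robust standard errors with a small-sample correction are an alternative. A fixed effect for each town will not serve, because town determines group.
- Report towns per arm, residents per town, and the ICC for each ATTID-SF factor.
- Restate power with a design effect, giving the assumed ICC and town count.

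**Cost.** Revised SAP wording and a re-run in the same software. Town of residence defined eligibility and group, so it should be recoverable, although the document does not say that it was stored. Intervals will be wider. The document is dated July 2025 and the last follow-up ended in December 2023, so the change must be reported as a post hoc re-analysis. It does not remove confounding from the non-random allocation.
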